#### **Session 4: MRI**

The fourth session will be an MRI Scan. It is anticipated that the complete session will take  $\sim$ 3 hours to complete, with less than 60 minutes in the scanner. Participants will be scheduled for the MRI scan and standard sequences will be collected that will consist of images of brain structure and function.

This session will take place at the BRain Imaging Data Generation & Education (BRIDGE) MRI Center located at the Mellon Institute and will be conducted by a trained researcher. Once at the center, participants will have their seated BP and HR taken, and they will receive training for the MRI protocol that will be administered. An additional screening for MRI eligibility will take place as a safety precaution, in addition to a pregnancy test (if necessary). Participants will also be asked to remove any piercings and completely empty their pockets of all contents. They will be given ear protection against the sound of the MRI machine and asked if they need to use the restroom before beginning.

Subjects will also be equipped with physiological monitoring (EKG sensors, a respiration belt, and a BP cuff) devices before being put into the scanner. The total time in the scanner will not exceed 60 minutes.

#### MRI Protocol:

Structural MRI sequences: Several structural sequences will be collected that will provide detailed information about brain morphology (T1 MPRAGE sequence) and hippocampal morphology (high-resolution hippocampal sequence). During these scans, participants will be asked to lay still and relax quietly.

Functional MRI sequences: Participants will be trained in all functional MRI scan tasks prior to entering the scanner.

Participants will use a mirror and back-projection screen system with a response glove. Participants will be able to view a screen at the back of the scanner via a mirror fixed to the head coil. They will be given a response glove to wear in each hand with buttons located under each finger. Depending on the functional MRI task, participants will be instructed to press one of 4 buttons underneath the middle and index fingers of their left and right hands.

Two functional MRI scans will involve identifying visual targets by pressing the correct button on a response box. For example, in one task, participants will see a series of color words (red, blue, yellow, green) and will be instructed to identify the color in which the word is presented as quickly as possible using response buttons on a key pad. In a second task, the participants will see numbers and will be asked to identify which one is different from the others. In the final task, subjects will view pictures of people and scenes. When viewing the pictures, they will be instructed to either allow themselves to experience any resulting emotions they feel about the picture naturally or to change how they feel by thinking differently about the picture. For example, when viewing a picture of a person in a hospital bed, then they can think of a quick and speedy recovery for that person. This is also called positive re-framing. As some subjects may find the nature of some of the pictures upsetting (e.g., they may feel disgusted if they see a picture of a dirty floor), we will allow them to view sample pictures before the MRI to prepare them. Only subjects who agree to view the pictures after practicing the task will be administered this paradigm during the scan. Participants completing the picture paradigm will also complete the Post-Task Questionnaire which assesses the strategies that were used to change their feelings about the pictures during the task.

An additional functional scan will be taken while the participant is at rest. The participant will be instructed to relax and lie still while looking at a fixation cross on a screen while remaining awake. This scan provides information on the brain networks involved while an individual is at rest.

Participants will be reminded periodically that they can discontinue the MRI protocol at any time. This will be done by a two-way communication system that allows for continuous monitoring and verbal exchanges with the participant throughout the MRI protocol. However, discontinuation of the MRI session may make them ineligible for continuation in the study.

Participants will be asked to provide subjective ratings of valence (1=very unhappy; 9=very happy), arousal (1=very calm; 9=very excited), and control (1=not at all; 9=very) during the MRI protocol. Participants will be familiarized with these rating scales beforehand.

All participants will be given a squeeze ball to press in the event that they want to end the scan for any reason. An alarm will sound in the control room and the technician will stop the scan and remove the participant from the scanner immediately.

#### 1.5.4 POST RANDOMIZATION TASKS:

Actigraph Link will be worn for one week every 6 weeks for each study participant. Measures of exercise self-efficacy are collected during the 3rd week of the intervention protocol.

#### **1.5.5** TIME POINT 2 (6 months):

At 6-months into the exercise sessions, the participants will complete the assessments that were conducted at baseline. These assessments should be completed within a 1 month window; therefore 2 weeks before their midpoint date or 2 weeks after their midpoint date. The EMA measurement will be completed at month 5 to ensure all other key physiological assessments are completed on time.

#### 1.5.6 TIME POINT 3 (12 months – post intervention):

At the 12-month session, participants will complete all the assessments that were done at baseline and 6 months. These assessments should be completed within a 1-month window; therefore 2 weeks before their end date or 2 weeks after their end date. It is encouraged to complete session 1 and session 2 within 2 weeks of the intervention completion. If someone is going on vacation after the intervention, then they may be brought in during their last week of intervention for the 12-month assessments. The EMA assessment will begin at Month 11 to ensure all other key physiological assessments are completed on time.

#### 1.6 **RANDOMIZATION**:

After the completion of the baseline measures and sessions described above the participants will be randomly assigned to one of two groups. These include (a) an exercise condition that will consist of 150 minutes per week of moderate-to-vigorous intensity exercise, or (b) a PA and health information group. We will use a computer randomization protocol that will incorporate a verification that all session visits have been completed and data entered into the database. We will use a minimization algorithm with equal allocation to one of the two groups. The use of the minimization strategy will ensure treatment balance on the two factors of age at study entry (=<42, >42) and gender. Once randomized, an assigned staff member will contact the participant via phone with the group information. On this contact, the staff member will give information such as date, day, time, and location of the subject's first intervention session.

#### 1.7 TARGETED ENROLLMENT TABLE

	September	October	November	December	January	Febuary	March	April	May	June			
Target (random)	planning/			procedures development				2	2	2			6
Enrolled													
Randomized													
Year 2													
	July	August	September	October	November	December	January	February	March	April	May	June	
Target (random)	2	3	3	3	3	3	4	6	7	7	7	5	53
Enrolled													
Randomized													
Year 3													
	July	August	September	October	November	December	January	February	March	April	May	June	
Target (random)	4	4	7	7	5	3	4	7	8	8	8	6	71
Enrolled													
Randomized													
Year 4													
	July	August	September	October	November	December	January	February	March	April	May	June	
Target (random)	6	7	7										20
Enrolled													
Randomized													
Year 5													
	July	August	September	October	November	December	January	February	March	April	May	June	

#### 1.8 INTERVENTION:

1.8.1 AEROBIC EXERCISE GROUP: Participants in the aerobic exercise condition will begin at a lighter intensity (50-60% Heart Rate Reserve or HRR) for 15-20 minutes during the first week of the program and gradually increase their intensity and duration by 5 minutes each subsequent week until they reach 60 minutes of exercise depending on the group (see more below). All exercise sessions start and end with 5-10 minutes of stretching for the purpose of warming up and cooling down. Levels of exercise intensity will be prescribed based upon maximal responses during the initial graded exercise treadmill test and then reassessed after the midpoint graded exercise treadmill test. As the participants will be low active at baseline, the prescribed intensity will be 50–60% of the maximum heart rate reserve for weeks one to six and 75–85% for the remainder of the program as long as it is deemed safe by the monitoring exercise physiologist and trainer. Participants that feel comfortable increasing their levels at a more rapid pace will be allowed to do so if the accompanying trainer also agrees that it is safe. Participants in the aerobic group will wear a heart rate monitor and be encouraged to exercise within their target heart rate zone. Heart rate intensity will be measured by a Polar H10 heart rate strap that is worn below their chest. Certified exercise instructors will closely monitor attendance, intensity, frequency, and safety. On-site exercise sessions will occur two days/week for the duration of the intervention and at home for one other day of the week. Compliance to home-based exercise will be monitored by exercise diaries.

**1.8.2 PHYSICAL ACTIVITY & HEALTH INFORMATION GROUP:** The control group will be asked to wear an ActiGraph daily monitor for 7 days every 6 weeks. They will not be given any information on exercise and they will not be asked to change their behavior or exercise patterns.

**1.8.3 EXERCISE COMPLIANCE:** Participants in the study will be completing part of the exercise under supervised conditions and part of the exercise under unsupervised conditions (e.g., home exercise). Monitoring compliance during the supervised exercise is relatively straightforward because we will have trainers monitoring attendance, duration of exercise, perceived exertion, mode of activity, and heart rate intensity throughout the period. However, compliance during the unsupervised sessions (~30 minutes) is inherently more challenging. In this study, we have proposed a two-faceted approach for monitoring compliance during the unsupervised periods. First, within the first few weeks of the intervention, our staff will train participants on the Ratings of Perceived Exertion (RPE) Scale and participants will be instructed to keep weekly diaries of the times, durations, and RPE intensity during the unsupervised exercise that they engage in. These diaries will then be collected on a weekly basis and entered into our database (REDcap). These diaries are a natural component of training since training involves the identification of barriers and approaches to overcoming non-compliance while keeping individuals engaged and continuing to return for the sessions.

In addition to the self-reported diaries of unsupervised exercise, we will have participants wear an Actigraph accelerometer for 1 week every 6 weeks of the study for 12 months (~9 weeks of accelerometer data). We will be able to use these data as objective confirmation that when participants are recording their exercise they are doing the activity at the prescribed intensity and for the prescribed duration. These assessments are important for providing an objective assessment of compliance during the unsupervised exercise periods.

Based on the above, we have operationally defined compliance to the intervention as those participants meeting the prescription of an average of 150 minutes per week of moderate-to-vigorous intensity exercise. Compliance to these prescriptions will be based on the information gathered from the weekly diaries, the supervised exercise sessions, and the accelerometer recordings. We will record on a weekly basis for each participant whether they were compliant or not.

Our analysis plan has proposed an intent-to-treat analysis where all participants, regardless of whether they complete all sessions, will be invited to return for follow-up assessments. However, there will likely be some participants that refuse to return for follow-up assessments or miss a mid-point assessment. "Lost to follow up" will be defined here as missing data that is contributing to the primary outcomes. The reason will be recorded (i.e., missed visit due to traveling, illness). These criteria and documentation will also be applied for any discontinued subjects with the reasons for discontinuation being recorded (i.e., moving out of state).

Regarding the analytical approach, we propose to use all available data in the planned analysis for testing our primary outcome. Since we are examining changes over time we will be able to conduct the analysis as long as there is at

least one follow-up assessment (either at the 6-month time point or the 12-month time point). We will assess the missingness of data consistent with the assumptions of the modeling approach described above. That is, we will examine the randomness of missing data and determine if the data is missing completely at random (MCAR) or missing at random (MAR) and use maximum likelihood estimation for computation of unbiased parameters estimates and standard errors. We will not conduct multiple imputation to correct for missing data.

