
sufficiently powered to test our hypotheses using structural equation modeling even after attrition. In sum, our planned sample size of 150 (N=75 per group) will be sufficient for allowing us to test our primary hypotheses.

**1.4.2. PRELIMINARY STEPS**: Prior to hypothesis testing, all data will be examined to determine: 1) frequency distributions for missing data and out-of-range values; 2) normality and internal consistency of subscales; and, 3) association between variables that may be highly correlated to guard against multicolinearity, which would inflate standard errors and make estimation

[figure not shown]

Figure 1. Diagram of exemplar full longitudinal mediational model. Paths involved in estimating longitudinal stability and residualized change are in black, paths involved in mediation are in red, and non-essential parameters are grayed out for legibility.

unstable. We will also examine the distribution of factors between groups to assess whether covariate-adjustment is required. Missing data: All outcomes will be tested using an intent-totreat (ITT) framework. Sensitivity will be explored using adherence to the intervention (e.g., per protocol). We will report reasons for dropouts and explore missing data mechanisms. To examine whether missingness is unrelated to other observed and unobserved measurements (missing completely at random, MCAR) or to the observed measurements only (missing at random, MAR), testing for completely random dropouts will be carried out. Additional sensitivity analyses test for informative dropouts. We will apply pattern-

mixture models by stratifying our data by dropout patterns and fitting separate regression models to strata.

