- Our original targeted sample size of 150 was re-evaluated by our study statistician ([name], Department of Biostatistics, University of Pittsburgh) with a focus on the minimal sample size needed to be sufficiently powered to test our primary hypotheses. Based on prior literature described in the grant application, we estimated effect sizes between .5 and .6 (Cohen's d) for changes in brain volume resulting from an exercise intervention. Using mixed effects modeling of the data in an intent-to-treat approach, we will have between 68-83% power to test our primary aim (hippocampal volume change) with 120 participants, which accounts for a possible 20% attrition rate. Similar effect sizes for the effects of exercise on various cardiovascular disease biomarkers have been reported (between .58 and .6). Therefore, a sample of 120 would provide us >80% power even with 20% attrition to test our hypotheses about the effects of exercise on cardiovascular disease biomarkers and mediators. In addition, we will be sufficiently powered (>80%) to test several of our secondary aims (e.g., depressive symptoms and functional brain connectivity) with a targeted sample of 120. In sum, we have determined that we will have sufficient power to test our primary aims with a reduction in the targeted sample size to 120. What is more at risk with a reduction in sample size is the statistical power for mediation analyses to test our tertiary aims (i.e., to use structural equation modeling approaches for examining mediators between changes in brain and changes in cardiovascular health markers). As such, we propose to move forward by conducting these tertiary aims on an exploratory basis.
- The power estimations described above include an attrition rate of 20%, but our current attrition rate is <10% for all participants that were not disrupted due to COVID. This suggests that the power estimations described above are likely conservative estimates.
- Our current exercise adherence and compliance rates are >90% indicating that we are successful at getting and keeping participants physically active. This is important because low adherence and compliance have a direct effect on our ability to test our hypotheses (i.e., if participants are not
- adherent then we would be unable to test our aims). In short, the exercise sessions and intervention are going well which supports our ability to test our primary and secondary aims with a smaller than originally proposed sample.

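### The 150-minute compliance rule makes no allowance for the ramp-up, so participants who follow the standard schedule exactly are recorded as non-compliant in the early weeks and, with a home session of about 30 minutes, over the year

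*Combined protocol and SAP*

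**What the plan says.** Section 1.8.1 sets the schedule. Participants "will begin at a lighter intensity (50-60% Heart Rate Reserve or HRR) for 15-20 minutes during the first week of the program" and then "gradually increase their intensity and duration by 5 minutes each subsequent week until they reach 60 minutes of exercise depending on the group"; the sentence points to later text for detail. On frequency: "On-site exercise sessions will occur two days/week for the duration of the intervention and at home for one other day of the week". A faster progression is allowed if the participant is comfortable and the trainer agrees that it is safe.

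Section 1.8.3 gives the length of the home session in passing: "compliance during the unsupervised sessions (~30 minutes) is inherently more challenging". It defines a compliant participant as one "meeting the prescription of an average of 150 minutes per week of moderate-to-vigorous intensity exercise", judged from diaries, supervised-session records and accelerometry. It adds: "We will record on a weekly basis for each participant whether they were compliant or not". It states no averaging window, no treatment of ramp weeks and no tolerance below 150.

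Sections 1.0 and 1.6 both give the dose of the exercise arm as 150 minutes per week.

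Adherence is used in two places. Section 1.4.2 says: "Sensitivity will be explored using adherence to the intervention (e.g., per protocol". The amendment section at the end of the document, supporting the reduction from 150 to 120 participants, says: "Our current exercise adherence and compliance rates are >90" (per cent), without defining the metric.

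**The concern.** A compliance rule should class someone who does exactly what was prescribed as compliant. Here the threshold appears to equal the highest weekly total that the schedule ever reaches, while the schedule spends its first weeks well below it. An average that includes any of those weeks must then fall short, and each ramp week fails if its yes/no record is read against 150.

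Two things are at stake. If the adherence analysis in 1.4.2 takes its definition from 1.8.3, the only operational definition in the document, it would remove people who followed the standard schedule and keep those who progressed faster or exercised more than was asked. That is selection on behaviour after randomization. Otherwise a window or tolerance would have to be chosen after the data are in. Second, the compliance percentage reported in the amendment is hard to interpret unless the reader knows whether ramp weeks count against participants.

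**Working it through.** **Inputs.** From 1.8.1: start S = 15 or 20 minutes, step 5 minutes per week, ceiling 60, two on-site sessions and one home session. From 1.8.3: home session about 30 minutes, threshold 150 min/week. From 1.0: 12 months. Assumptions: 12 months is 52 weeks, and the weekly yes/no record compares that week's total with 150.

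**The plan's own dose.** 2 × 60 + 30 = 150 min/week. This matches the stated dose, so a home session of about 30 minutes is the reading on which 1.8.1 and 1.8.3 agree.

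**Formula.** Session length in week w is min(60, S + 5(w − 1)). Weekly total = 2 × session + home. The yearly mean is the plateau minus (sum of weekly shortfalls)/52.

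**Reading A: home session about 30 minutes, plateau 150.**

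- S = 15: 60 minutes is reached in week 10. Shortfall per on-site session over weeks 1-9 is 45 + 40 + … + 5 = 225, or 450 for two sessions. Mean = 150 − 450/52 = 141.3. If the home session also builds up to 30 (15, 20, 25, then 30), add 15 + 10 + 5 = 30: mean = 150 − 480/52 = 140.8.
- S = 20: 60 minutes is reached in week 9. Shortfall over weeks 1-8 is 40 + 35 + … + 5 = 180, or 360 for two. Mean = 150 − 360/52 = 143.1. With the home session building up, add 10 + 5 = 15: mean = 150 − 375/52 = 142.8.
- Weeks at 150: 52 − 9 = 43 (83%) or 52 − 8 = 44 (85%).

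**Reading B: the home session also rises to 60, plateau 180.**

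- S = 15: mean = 180 − 3 × 225/52 = 167.0. The total reaches 150 when sessions reach 50 minutes, in week 8, so weeks 1-7 fail and 45 of 52 pass (87%).
- S = 20: mean = 180 − 3 × 180/52 = 169.6. Weeks 1-6 fail and 46 of 52 pass (88%).

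| | Yearly mean (min/week) | Weeks at or above 150 |
|---|---|---|
| A, S = 15 | 140.8-141.3 | 43/52 |
| A, S = 20 | 142.8-143.1 | 44/52 |
| B, S = 15 | 167.0 | 45/52 |
| B, S = 20 | 169.6 | 46/52 |

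**Sensitivity of reading A.**

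- Counting 48 weeks instead of 52 gives a mean of 140.0-142.5.
- If the lighter-intensity weeks 1-6 were not credited as moderate-to-vigorous, the 52-week mean would be about 131-132.
- A jump to 60 minutes in week 2 gives about 148. Weekly totals never exceed 150, so no window containing a ramp week can average 150 from scheduled minutes alone.
- With 10-minute steps, as an illustration, 150 is reached in week 5 (S = 20) or week 6 (S = 15). Then 48/52 = 92% or 47/52 = 90.4% of weeks pass.

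**The case against.** The strongest reply is that the shortfall depends on a reading. It needs a home session held near 30 minutes and an average that includes the ramp, and the plan states no window. A post-ramp window would give exactly 150. The home figure is approximate, and about 37-40 minutes would close the gap. So would 7-9 minutes a week of extra exercise, which the diaries could capture. The references in 1.8.3 to prescriptions could also be taken to mean each week's own prescription. All of this is fair, and it makes the yearly result conditional. It does not rescue the weekly record, which fails in the ramp weeks on both readings when held to 150, and none of these allowances is written down.

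Three stronger inferences are tempting, and the documents do not support them.

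- *Sections 1.8.1 and 1.8.3 contradict each other outright.* They do not: 60 + 60 + about 30 gives the stated dose. The session lengths conflict only if the home session also rises to 60.
- *The compliance rate above 90% cannot be on the weekly definition.* The 83-85% applies to exact adherence to the standard ramp. The permitted faster progression can put more than 90% of weeks at 150, and extra exercise could too. The amendment's metric is undefined and could be attendance, the share of participants, or completed over prescribed minutes. The reduced sample size rests mainly on effect sizes and power; adherence is supporting text.
- *The per-protocol set will exclude people who followed the schedule.* Section 1.4.2 offers per protocol only as an example, defines no such set, and does not name the 150-minute rule as its entry criterion.

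**Conclusion.** The point holds as a defect in the written compliance rule. With a home session of about 30 minutes, exact adherence to the standard ramp averages about 141-143 min/week over 52 weeks, some 5-6% below the threshold, and meets it in 43-44 of 52 weeks. If all three sessions reach 60 minutes, the yearly average passes but 6 or 7 weeks are still recorded as non-compliant. These figures assume a 52-week year, credit for the lighter early weeks, no extra exercise, and 150 as the weekly criterion.

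The consequence is limited to adherence-based sensitivity analyses that adopt this rule and to the interpretation of reported compliance. The intent-to-treat primary analysis does not use it. The correction is worth making because it is cheap and because, left alone, it invites either misclassification or a definition chosen after the fact.

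**What to change.** In 1.8.3, score each week as minutes completed divided by minutes prescribed for that week. Use session records for supervised exercise, and diary duration, RPE and accelerometry for home exercise; no section describes home heart-rate data being used to score compliance. State which schedule supplies the denominator when a participant progresses faster than standard. In 1.4.2, define per-protocol status by a cut-off on the mean ratio over the year, fixed before outcomes are analysed.

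In the amendment section, state which metric the figure above 90% uses, and restate it on the new definition.

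The sponsor should reconcile the home-session length between 1.8.1 and 1.8.3, including the pointer in 1.8.1 to later detail by group, which nothing later resolves. No session length is proposed here.

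The cost is protocol and SAP wording plus recoding of data the plan already collects. Accelerometry covers only one week in six, so home intensity will rest mainly on diary RPE. The reported compliance percentage may change.
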